6.7. STATISTICAL TESTS

The primary analysis of the primary endpoint will be conducted using a one-sided test with a 0.1 significance level. All other PFS analyses will be conducted using one-sided tests with a 0.1 significance level also. Secondary endpoints such as OS, ORR, DCR, and DOR will be analyzed using two-sided tests with a significance level of 0.05.

6.8. COMMON CALCULATIONS

For quantitative measurements, change from baseline will be calculated as:

- Change from Baseline = Test Value at Visit X – Baseline Value
- Percent Change from Baseline = $100 \times (\text{Test Value at Visit X} - \text{Baseline Value}) / \text{Baseline Value}$

6.9. SOFTWARE VERSION

All analyses will be conducted using SAS version 9.4 or higher. PK analysis will be conducted by the sponsor, using Phoenix™ WinNonlin® Build 6.2.1.51 (Pharsight Corp., Mountain View, CA).

7. STATISTICAL CONSIDERATIONS

7.1. ADJUSTMENTS FOR COVARIATES AND FACTORS TO BE INCLUDED IN ANALYSES

7.1.1. RANDOMIZATION STRATIFICATION FACTORS

The ECOG PS (0, 1), the RCC histological type (clear cell, non-clear cell), and the number of prior systemic RCC regimens (2 for clear cell or 1 for non-clear cell; >2 for clear cell or >1 for non-clear cell) are stratification factors in the randomization.

Two of these stratification factors will be used in the inferential comparisons of the primary and secondary efficacy endpoints between the treatment groups: ECOG PS (0 or 1) and the number of prior systemic RCC regimens (2 for clear cell or 1 for non-clear cell; >2 for clear cell or >1 for non-clear cell). Histology will not be used as a stratification variable in the inferential analyses due to the limited number of non-clear cell subjects expected to be enrolled into the study.

The stratification factor values used to randomize subjects will be obtained from the IRT and will serve to define the strata for the analyses as follows:

- Stratum 1: ECOG-PS = 0 and number of prior systemic RCC regimens = 2 for clear cell or 1 for non-clear cell
- Stratum 2: ECOG-PS = 0 and number of prior systemic RCC regimens = >2 for clear cell or >1 for non-clear cell
- Stratum 3: ECOG-PS = 1 and number of prior systemic RCC regimens = 2 for clear cell or 1 for non-clear cell
- Stratum 4: ECOG-PS = 1 and number of prior systemic RCC regimens = >2 for clear cell or >1 for non-clear cell

7.1.2. DEMOGRAPHIC AND OTHER BASELINE CHARACTERISTICS

The following demographic and other baseline characteristics will be used as covariates in exploratory subgroup analyses (Section 7.6):

- Age group
- Gender
- Race
- ECOG-PS at baseline
- RCC Histology
- Number of prior systemic cancer treatment regimens for RCC

7.1.3. PROGNOSTIC RISK GROUP

A prognostic risk group based on the International Metastatic RCC Database Consortium (IMDC) using Heng's 6 prognostic criteria (Heng et al, 2009) is planned for use in selected sensitivity and exploratory subgroup analyses. Heng's prognostic criteria are:

- Karnofsky Performance Score (KPS) <80
- Hemoglobin < lower limit of normal (LLN)
- Time from diagnosis to first line treatment <1 year
- Corrected calcium > upper limit of normal (ULN)
- Platelets > ULN.
- Neutrophil count > ULN

The prognostic risk groups are defined as favorable (0 factors), intermediate (1-2 factors), or poor (≥ 3 factors).

As the current study collects the ECOG Performance Status rather than the Karnofsky Performance Status (KPS), it is necessary to equate the scores from the two scales. For the purpose of defining the prognostic risk group, the two scales will be mapped as published by Oken et al (1982) and shown in Table C. Accordingly, a Karnofsky score <80 will be considered equivalent to an ECOG score >1.

Table C. Mapping of Karnofsky Performance Score to ECOG Performance Status

Karnofsky Performance Status	ECOG Performance Status
100 - Normal; no complaints	0 – Asymptomatic (Fully active, able to carry on all pre-disease activities without restriction)
90 - Able to carry on normal activity. Minor signs or symptoms of disease	1 – Symptomatic but completely ambulatory (Restricted in physically strenuous activity but ambulatory and able to carry out work of a light or sedentary nature, e.g., light housework, office work)
80 - Normal activity with effort	
70 - Care for self. Unable to carry on normal activity or to do active work	2 – Symptomatic, <50% in bed during the day (Ambulatory and capable of all self-care but unable to carry out any work activities. Up and about more than 50% of waking hours)
60 - Requires occasional assistance, but is able to care for most of his needs	
50 - Requires considerable assistance and frequent medical care	3 – Symptomatic, >50% in bed, but not bedbound (Capable of only limited self-care, confined to bed or chair more than 50% of waking hours)
40 - Disabled; requires special care and assistance	
30 - Severely disabled. Hospitalization indicated though death not imminent	4 – Bedbound (Completely disabled. Cannot carry on any self-care. Totally confined to bed or chair)
20 - Very sick; hospitalization necessary. Active supportive treatment necessary	
10 - Moribund	
0 - Dead	5 - Dead

No other covariates are planned for inclusion in primary, secondary, or sensitivity analyses. However, see Section 7.6 for a more complete list of factors that may be used for exploratory subgroup analyses.

7.2. MULTICENTER STUDIES

Approximately 30 sites (United States, Canada) are planned to participate in this study. Each site is expected to enroll at least 4 subjects in this study. Sites that do not enroll a subject ≤ 3 months from the study initiation visit date may be terminated and replaced.

Randomization to treatment arms is centralized across all countries and study sites. No examination of treatment by center interaction will be performed.

7.3. MISSING DATA

Table D describes where to find the discussions of missing data imputation rules for different types of data.

Table D. Location of Imputation Rules in This Document

Imputation Type	Notes/Location in this document
Incomplete start or end dates for prior/concomitant medications	Appendix 2
Missing study drug data	Section 15 and Section 16
Missing efficacy data	Section 17, imputation of individual endpoints, including consideration of multiple censoring criteria for use in the analysis of PFS
Incomplete AE data	Section 19.1, missing severity or other event characteristics. Appendix 2, imputation of missing/incomplete dates.
Other safety data	Respective part of Section 19.

7.4. MULTIPLE COMPARISONS/MULTIPLICITY

Analyses will be performed twice during this study. The main analysis will be conducted and conclusions about efficacy will be made when approximately 110 PFS events have occurred. No adjustment of the alpha used in the Main Analysis will be made due to conducting the End of Study Analysis.

As this is a two-arm study with one primary end point, no adjustment for multiple endpoints or multiple comparisons will be required for the primary analysis.

Since the secondary endpoints do not have a natural hierarchy and there is limited power for these tests, nominal p-values will be reported, which means that no formal adjustment for multiplicity will be done. However, if substantial differences in results among these endpoints are observed, reporting of results will include specific statements acknowledging the increase in type 1 error inherent in situations with multiple comparisons.

7.5. ACTIVE-CONTROL STUDIES INTENDED TO SHOW NON-INFERIORITY OR EQUIVALENCE

Not applicable. This is an active-controlled trial designed to show that AGS-16C3F is superior to axitinib. The primary analysis of PFS is based on one-sided test conducted at the .10 level. Details of the primary analysis are provided in Section 17.1.3.

7.6. EXAMINATION OF SUBGROUPS

7.6.1. SUBGROUPS AT BASELINE

Demographics and other baseline characteristics, disease history, prior cancer treatment history, prior cancer systemic therapy, and prior cancer radiotherapy will be summarized by treatment arm and histological group (clear cell, non-clear cell) in the FAS.

7.6.2. SUBGROUPS FOR EFFICACY

This study was not designed to detect treatment differences within subgroups with high statistical power. However, subgroup analyses may be performed for selected baseline characteristics for the purpose of hypothesis generation.

In particular, exploratory subgroup analyses may be conducted to assess potential heterogeneity of treatment effects across levels of baseline characteristics such as age, gender, race, ECOG PS, the number of prior systemic RCC regimens, histological group, and risk group. Analyses will be performed for the FAS. Each analysis will include only treatment, a single exploratory variable, and their interaction. The following subgroups will be assessed.

- Gender
 - o Female
 - o Male (*)
- Age (years)
 - o <65 (*)
 - o ≥65
- Race in 2 categories
 - o Caucasian (*)
 - o Other
- ECOG Performance Status
 - o 0
 - o 1 (*)
- Histology
 - o Clear cell (*)
 - o Non-clear cell
- Number of prior systemic RCC regimens
 - o 2 if clear cell or 1 if non-clear cell (*)
 - o >2 if clear cell or >1 if non-clear cell
- Prognostic risk group (Heng's criteria, see Section 7.1.3)
 - o Favorable (0 risk factors)
 - o Intermediate (1-2 risk factors)
 - o Poor (≥3 risk factors) (*)

Note: (*) Indicates the reference group for statistical models.

8. OUTPUT PRESENTATIONS

Appendix 1 describes the conventions for presentation of data in outputs.

The templates provided with this SAP describe the presentations for this study and therefore the format and content of the summary tables, figures and listings to be provided by Quintiles Biostatistics.

All collected data will be displayed in listings, unless otherwise specified in Section 22.

9. DISPOSITION AND WITHDRAWALS

There is expected to be a pre-screening informed consent and a main informed consent. Only subjects who sign the main consent and are randomized are considered to be enrolled. The set of randomized subjects will be identical to the FAS.

The number and percentage of FAS subjects who are continuing in the study or were discontinued from the study (by primary reason for discontinuation), and the number and percentage who are continuing treatment or were discontinued from treatment (by primary reason for discontinuation) will be presented by treatment group and overall.

10. PROTOCOL DEVIATIONS AND SUBJECT EXCLUSIONS FROM ANALYSES

All protocol deviations are recorded in the Clinical Trial Management System (CTMS). Only the protocol deviations that are determined to be statistically important protocol deviations, which are defined to include those described in Protocol Section 7.7 and Protocol Section 8.1.6, will be presented on tables and listings for the clinical study report. The statistically important deviations will be summarized by treatment arm and overall, using the number and percentage of subjects who had each type of deviation. A summary by study site will also be produced.

Subject exclusions and reasons for exclusion from analysis sets will be summarized by treatment arm and overall. See also Section 5, "Analysis Sets", for the list of statistically important deviations that could affect efficacy outcomes, as these are the particular important deviations which could result in subject exclusion from some analyses.

11. DEMOGRAPHIC AND OTHER BASELINE CHARACTERISTICS

Detailed information on subject demographics and other baseline characteristics will be reported. Descriptive statistics will be generated by treatment group and overall. In the FAS, summary statistics will be produced for all FAS subjects and by grouped histological type. In the PPS and SAF, summary statistics will be produced only for all subjects in the analysis set. If the analysis sets are identical the tables will only be presented only once in the CSR. No statistical testing will be carried out for demographic or other baseline characteristics.

The following demographic and other baseline characteristics will be reported for this study:

- Sex (male, female)
- If female, child-bearing potential
- Ethnicity (Hispanic or Latino, not Hispanic or Latino)
- Race (white, black or Afro-American, Asian, American Indian or Alaska Native, Native Hawaiian or other Pacific Islander, Other)
- Age (years) at Cycle 1 Day 1
- Age group (<65 years, ≥65 years)
- Baseline height (cm)
- Baseline weight (kg)
- BMI (kg/m²)
- BMI group (<18.5, 18.5 to <30, ≥30)

The following additional baseline characteristics will be reported on the same table:

- ECOG Performance Status (0, 1)
- Grouped histological type (clear cell, non-clear cell)
- Number of prior systemic RCC regimens (2 if clear cell or 1 if non-clear cell, >2 if clear cell or >1 if non-clear cell)
- Prognosis risk group (favorable, intermediate, poor), based on Heng's criteria; see Section 7.1.3.

11.1. DERIVATIONS RELATED TO DEMOGRAPHIC AND BASELINE CHARACTERISTICS

- $BMI (kg/m^2) = \text{weight (kg)} / \text{height (m)}^2$

12. SURGICAL AND MEDICAL HISTORY

Surgical and medical history conditions are defined as those conditions which start prior to the date of first dose of study drug and stop prior to or on the date of first dose of study drug. A detailed surgical and medical history will be obtained for each subject during the screening period. Where applicable, medical conditions and events will be coded to a preferred term using MedDRA version 18.1.

The following types of surgical and medical history will be collected in the eCRFs and reported for the FAS, PPS, and SAF in this study.

- Disease History
- Prior Cancer Treatment History
- Prior Cancer Systemic History
- Prior Cancer Radiotherapy
- Ocular Symptom History
- Medical History

12.1. DISEASE HISTORY

Data collected on renal cell carcinoma diagnosis, metastasis, histology, and additional relevant biological information will be summarized by treatment group and overall. In the FAS, summary statistics will be produced for all FAS subjects and by grouped histological type. In the PPS and SAF, summary statistics will be produced only for all subjects in the analysis set. Each subject's complete cancer history will be listed.

The following information related to renal cell carcinoma diagnosis, metastasis, histology, and additional relevant biological information will be collected on the disease history eCRF.

- Time since diagnosis (years), calculated relative to date of randomization
- Type of solid tumor cancer
- Histological type

- TNM stage at initial diagnosis, based on AJCC 7th edition (Stage I, II, III, IV, Unknown; and individual T, N, M codes)
- Time in years since diagnosis of metastatic disease, calculated relative to date of randomization

Summary statistics will be generated by treatment group and overall. In the FAS, summary statistics will be produced for all FAS subjects and by grouped histological type. In the PPS and SAF, summary statistics will be produced only for all subjects in the analysis set.

Time since diagnosis of RCC and time since diagnosis of metastatic disease will be summarized by treatment arm using descriptive statistics for continuous measures. For other items, the number and percent of subjects who gave each pre-printed response will be presented by treatment arm (see eCRF or mock shells for the list of response choices).

12.2. PRIOR CANCER TREATMENT HISTORY

The following information will be collected on the eCRFs for prior cancer surgery and prior cancer radiotherapy.

- Prior Cancer Surgery
 - o Surgery for malignancy prior to enrollment (Y, N)
 - o Type of Surgery (Nephrectomy, Partial Nephrectomy, Other (specify))
- Prior Cancer Radiotherapy
 - o Radiotherapy for malignancy prior to enrolment (Y, N)
 - o Type of Radiation
 - o Site
 - o Start Date
 - o Stop Date

Summary statistics will be generated by treatment group and overall. In the FAS, the summary statistics will be produced for all FAS subjects and by grouped histological type. In the PPS and SAF, the summary statistics will be produced only for all subjects in the analysis set.

The number and percentage of subjects in each treatment arm who had any prior cancer surgery, and the number and percentage who had each type of surgery, will be reported using the pre-printed terms on the eCRF. All data, including the terms listed in the 'other (specify)' category, will be presented in a listing.

The number and percentage of subjects in each treatment arm who had any prior cancer radiotherapy, and the number and percentage who had each type of radiation, will be reported using the pre-printed terms on the eCRF. All data, including the terms listed in the 'other (specify)' category, the radiation site, and the therapy start and stop dates, will be presented in a listing.

12.3. PRIOR CANCER SYSTEMIC THERAPY

The following information will be collected on a Prior Cancer Systemic Therapy eCRF.

- Regimen number
- Treatment name (see eCRF list)
- Start date
- Stop date

Summary statistics will be generated by treatment group and overall. In the FAS, summary statistics will be produced for all subjects in the analysis set and by grouped histological type; this version of the table will also be produced in the SAF for the IDMC. In the PPS and SAF for the clinical study report, summary statistics will be produced only for all subjects in the analysis set.

The number and percentage of subjects who had each actual count of prior systemic RCC regimens (i.e., the number and percentage who had exactly 1 prior regimen, exactly 2 prior regimens, etc.) will be presented. The number and percentage of subjects who had each individual treatment and the number who had each distinct combination of drugs reported as a single regimen will be presented. All data, including the start and stop dates, will be presented in a listing.

12.4. OCULAR HISTORY

The following data will be collected on an Ocular History eCRF and coded using MedDRA Version 18.1.

- Any ocular history (Y, N)
- Diagnoses
- Start date
- Stop date/ongoing

Summary statistics will be generated by treatment group and overall for the FAS, PPS and SAF.

The number and percentage of subjects who had any ocular history and who had each type of ocular history will be summarized by treatment arm and PT. The PTs will be ordered alphabetically. The diagnoses will be presented as all diagnoses and diagnoses which were ongoing at the time the data were recorded. A data listing will be provided.

12.5. MEDICAL HISTORY

Medical history will be captured on the Medical History page of the eCRF and coded using MedDRA Version 18.1. Summary statistics will be produced for the FAS, PPS, and SAF.

The number and percentage of subjects who report any medical history (i.e., “any findings”), any condition in a specified SOC, or who report each unique PT, will be summarized by treatment arm. The SOC’s will be arranged alphabetically. Within SOC, the PTs will be arranged in order of descending frequency in the AGS-16C3F arm. The history will be presented as all medical history and conditions which were ongoing at the time the history was collected. A data listing will be provided.

13. CONCOMITANT PROCEDURES

Concomitant procedures are captured on a separate eCRF. They will be coded and summarized using the same dictionary (MedDRA Version 18.1) and methods as the medical history, as well as presented in a listing.

14. PREVIOUS AND CONCOMITANT MEDICATIONS

The protocol indicates that medications including dietary supplements taken from the time of informed consent through the last formal follow-up observational period should be recorded on the Concomitant Medications CRF. All recorded medications will be coded using the WHO drug dictionary version 01 Sep 2015.

Subsequent discussions indicated no interest in medications taken before the first dose of study medication. Therefore, recorded medications that were used on or after C1D1 will be classified as concomitant or post-treatment according to the definitions below; prior medications will be listed but will not be summarized.

Concomitant medications are medications which were used during the period of treatment with study drug, including:

- Medications that started prior to C1D1 and ended (or were ongoing) on or after C1D1
- Medications that started and ended on C1D1
- Medications that started on or after C1D1 and before a decision to discontinue treatment for AGS-16C3F subjects or before the last dose of study medication for axitinib subjects.

Post-treatment (or “post”) medications are medications that began on or after the date of a decision to discontinue study drug for AGS-16C3F subjects or after the last dose of study drug for axitinib subjects.

See Appendix 2 for handling of partial dates for medications. The status of each medication as a concomitant or post-treatment medication will be determined after the imputation of any partial or missing dates.

In cases where it is not possible to determine if a medication was used during or after the treatment period, the medication will be classified as a concomitant medication only.

The number and percent of subjects who used each type of concomitant medication, categorized by ATC Level 1 (Anatomical Main Group), ATC Level 4 (Chemical/therapeutic/pharmacological subgroup), and medicinal product (MP), will be summarized by treatment arm for the FAS, PPS and SAF. Post-treatment (“Post”) medications taken as part of a subsequent cancer treatment regimen for RCC will be summarized similarly and will be presented on a separate table.

All recorded medication data will be listed.

15. STUDY DRUG EXPOSURE

Algorithms described in this section could change to ensure the correct handling of unusual cases. Any such changes will be documented in the analysis dataset specifications.

All study drug exposure data will be presented in a listing.

15.1. AGS-16C3F

The following study drug parameters will be summarized for subjects who receive AGS-16C3F.

- Duration of treatment (weeks) in the study will be reported using descriptive statistics
- Amount of exposure to study drug during the study, expressed as number of doses received and total amount of drug used (mg), will be reported using descriptive statistics
- Number and percentage of subjects who required a dose reduction to 1.2 mg/kg
- Number and percentage of subjects who had any treatment delay (time since previous dose >28 days) due to toxicity (adverse event)), overall and by Cycle
- Descriptive statistics for the duration of treatment delays (defined as the time between two consecutive dosing visits in days minus 28 days)

15.1.1. DERIVATIONS RELATED TO AGS-16C3F EXPOSURE**15.1.1.1. Dates of First Dose and Last Dose of AGS-16C3F**

For subjects who receive AGS-16C3F, the date of first administration of study drug will be the earliest administration date recorded on the AGS-16C3F Drug Administration eCRF. The date of last administration of study drug will be the latest administration date recorded on the AGS-16C3F Drug Administration eCRF.

15.1.1.2. Duration of Treatment with AGS-16C3F

For subjects who are on treatment, the duration of treatment (days) will be calculated as the data cut-off date minus date of the first dose + 1. For subjects who have gone off treatment, the duration of treatment (days) will be calculated as the date decision made to end treatment (from the "Subject Status – Completion" eCRF) minus the date of the first dose + 1. In each case, the calculation will be made without consideration of interruptions, compliance, or dose changes. Delays between doses will be included, unless the subject discontinues from the study without resuming treatment.

Duration of treatment in days will be converted to duration of treatment in weeks, rounded to the closest 1/10) for summary tables and listings, using the following formula: Number of weeks = round ((number of days/7), 0.1).

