15.1.1.5. Definition and Calculation of Treatment Delay

The protocol-specified dosing schedule is one dose every 21 days. If for logistical reasons (e.g., public holidays, clinic scheduling, etc.) the next dose cannot be given 21 days from the last dose, a -2 day and a +7 day dosing window is allowed.

Therefore, a delay is defined to have occurred when a subject has >28 days:

- Between 2 consecutive doses, or
- Between the date of the last dose administered and the earlier of (the date of the decision to stop treatment or the data cut-off date).

When a treatment delay occurs, it will be attributed to the later of the two doses. The length of the delay will be calculated as the difference between the two dates, minus the planned cycle time.

For example, suppose that the dates of the Cycle 4 and Cycle 5 doses were 35 days apart. The delay which occurred between Cycle 4 and Cycle 5 would be identified as belonging to Cycle 5 in the analysis dataset. The length of the

delay would be calculated as the date of the Cycle 5 dose minus the date of the Cycle 4 dose minus 28 days; given that the two doses were 35 days apart, this means the length of the delay would be 7 days.

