15.2.1.2. Duration of Treatment with Axitinib

For subjects who are on treatment, the duration of treatment (days) will be calculated as the data cut-off date minus date of the first dose + 1. For subjects who have gone off treatment, the duration of treatment (days) will be calculated as the last dose date minus the date of the first dose + 1. In each case, the calculation will be made without consideration of interruptions, compliance, or dose changes. Treatment delay time will be included, unless the subject discontinues from the study without resuming treatment.

If the subject discontinues from study, is lost to follow-up, or dies, and the last dose date remains unavailable at the time of database lock or data cut-off, then the imputed date of last dose will be used in calculating the duration of treatment. Duration of treatment in days will be converted to duration of treatment in weeks, rounded to the closest 1/10) for summary tables and listings, using the following formula:

Number of weeks = round ((number of days/7), 0.1).

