19.7. OTHER SAFETY ASSESSMENTS

19.7.1. OPHTHALMOLOGIC EXAMS

A complete eye exam is planned to be performed at Baseline for all subjects, at end of Cycle 2, end of Cycle 6, and at Safety Follow-up for AGS-16C3F subjects, and at other times if clinically indicated for any subject. Results will be collected on the Eye Exam eCRF page. The following types of data will be collected.

- Ophthalmology Symptoms
- Visual Acuity
- Extraocular Movement
- Tonometry
- External Exam
- Slit Lamp Exam
- Dilated Fundus Exam
- Optional Exams
- Impression
- Visual Acuity Grade
- Ocular Diagnoses and Ophthalmology Outcome, including the diagnosis, event status (new, ongoing, resolved), relatedness to study drug, prescribed treatment, and action taken with study treatment due to the eye exam results.

In general, eye-related summaries by timepoint will include data from both planned and PRN assessments. Determinations at each timepoint will include all eye data collected since the previous planned assessment. The screening period will include eye assessments performed within 28 days prior to the first dose of study drug. For subjects who receive AGS-16C3F, Day 43 will include the worst value recorded for each subject from post-dose

C1D1 through Predose C3D1, inclusive. Day 106 will include the worst value recorded from Post-dose C3D1 through C6D1, inclusive. Subsequent intervals will be defined similarly at 3-cycle intervals during treatment. For subjects who receive axitinib, Day 43 will include the worst value recorded for each subject from Day 1 through Day 43 (± 7 days). Day 106 will include the worst value recorded from the Day 43 assessment date + 1 through Day 106 (± 7 days), inclusive. Subsequent intervals will be defined similarly at 63-day intervals during treatment. Data collected after the decision to end treatment for AGS-16C3F subjects or after the date of last dose for axitinib subjects are considered to be “end of treatment and beyond”.

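### The SAP's medication and eye-period rules end treatment on different dates in the two arms, and its AGS-16C3F duration rule contradicts itself on a final hold that is never resumed

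*SAP*

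**What the plan says.** For subjects who have gone off treatment, the SAP uses two end dates.

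- **Duration, AGS-16C3F (SAP 15.1.1.2):** "duration of treatment (days) will be calculated as the date decision made to end treatment", minus the first-dose date plus 1. The same paragraph then adds: "Delays between doses will be included, unless the subject discontinues from the study without resuming treatment".
- **Duration, axitinib (SAP 15.2.1.2):** "the duration of treatment (days) will be calculated as the last dose date minus the date of the first dose + 1". The parallel exception reads: "Treatment delay time will be included, unless the subject discontinues from the study without resuming treatment".
- **Medications (SAP 14, repeated in Appendix 2):** a drug started after C1D1 is concomitant if it began "before a decision to discontinue treatment for AGS-16C3F subjects or before the last dose of study medication for axitinib subjects". Post-treatment drugs are tabulated only if they belong to a subsequent RCC regimen. All recorded medications are listed.
- **Eye exams (SAP 19.7.1):** "Data collected after the decision to end treatment for AGS-16C3F subjects or after the date of last dose for axitinib subjects" go into a separate end-of-treatment period.
- **Treatment delay, AGS-16C3F (SAP 15.1.1.5):** a delay also exists when more than 28 days pass "Between the date of the last dose administered and the earlier of (the date of the decision to stop treatment" or the data cut-off.

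SAP 6.1 defines the treatment period with either end date and does not say which arm uses which. Subjects still on treatment are handled alike: SAP 15.1.1.2 states "For subjects who are on treatment, the duration of treatment (days) will be calculated as the data cut-off date minus date of the first dose" plus 1, and SAP 15.2.1.2 has the same rule.

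**The concern.** When a subject stops at progression, the decision and the end of drug cover lie close together and the choice of date matters little. It matters when drug is held and then never restarted. The protocol foresees this: Table 9 holds AGS-16C3F for Grade 3 thrombocytopenia and names permanent discontinuation as one outcome if there is no recovery within 5 weeks, and Table 10 holds treatment for Grade 3 ocular symptoms.

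During such a hold the two arms are on different clocks. Supportive drugs started to treat the toxicity are on-treatment events in one arm and post-treatment events in the other, and so are eye findings. The duration table may or may not share the problem, depending on which sentence of SAP 15.1.1.2 the programmer follows. Ocular safety is a stated objective in SAP 2.3, so the tables concerned will be read side by side.

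**Working it through.** **The SAP's own figure.** SAP 15.1.1.5 gives an example of two doses 35 days apart: 35 − 28 = 7 days of delay. This reproduces. The text there says to subtract the planned cycle time, which is 21 days and would give 14. The example and SAP 15.1 both subtract 28, so 28 is used below.

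**Illustrative subjects (assumed).** AGS-16C3F infusions on Days 1 and 22. With the 21-day cycle, cover runs to Day 22 + 20 = Day 42. Drug is held from Day 43 and the decision to stop comes on Day 77. The axitinib subject takes the last tablet on Day 42 and has the same hold and decision date.

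**Duration.**

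| Rule | AGS-16C3F | Axitinib |
|---|---|---|
| SAP formula | 77 − 1 + 1 = 77 days (11.0 weeks) | 42 − 1 + 1 = 42 days (6.0 weeks) |
| SAP exception, read as ending at last infusion | 22 days (3.1 weeks) | 42 days |
| SAP exception, read as ending with the last cycle | 42 days (6.0 weeks) | 42 days |

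The formula gives an excess of 77 − 42 = 35 days. Under the exception the hold drops out, but SAP 15.1.1.2 does not say which of the last two rows replaces it.

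**Other hold lengths, formula reading.** With infusions on Days 1, 22, 43 and 64, cover ends on Day 84. A decision on Day 92, 99, 106 or 120 gives 92, 99, 106 or 120 days for AGS-16C3F against 84 for axitinib, an excess of 8, 15, 22 or 36 days.

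**Effect on the arm mean, formula reading only.** The documents do not give the share of subjects who stop after such a hold. If it is 10% to 30% (assumed) and each hold lasts 5 weeks, mean AGS-16C3F duration rises by 0.10 × 5 = 0.5 to 0.30 × 5 = 1.5 weeks.

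**Delay.** From last infusion to decision is 77 − 22 = 55 days, which exceeds 28, so SAP 15.1.1.5 records 55 − 28 = 27 days of delay. On the formula reading these 27 days are also inside the treatment duration.

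**Medications.** A non-anticancer drug started on Day 60 precedes the decision, so it is concomitant and tabulated for AGS-16C3F. For axitinib it follows the last dose. It is therefore a post medication outside any RCC regimen and appears only in the listing.

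**Eye exams.** An exam on Day 60 belongs to a treatment interval for AGS-16C3F and to the end-of-treatment period for axitinib.

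**Symptom-free days (SAP 19.7.2).** The text says during treatment and gives no end date. If eye symptoms last from Day 22 to Day 42, the symptom-free share is (77 − 21)/77 = 73% on the decision-date clock and (42 − 21)/42 = 50% on the coverage clock. If they persist from Day 22 to Day 77, it is 21/77 = 27% against 21/42 = 50%. The sign reverses.

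**The case against.** A reader might infer that the SAP simply counts a terminal hold as AGS-16C3F treatment, so that 77 against 42 days is what it prescribes. The documents do not support that as a settled rule. Protocol 6.1 defines a discontinuation as permanent stopping of study treatment, and Protocol 5.5 speaks of subjects who discontinued the study while still being scanned. On that usage the exception in SAP 15.1.1.2 covers exactly this subject. SAP 15 also allows algorithms to change for unusual cases. This stands, and it reduces the duration point to a contradiction. It does not remove the point, because the exception leaves the end date open and a stop after a hold is foreseeable.

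A reader might also infer that AGS-16C3F eye toxicity is diluted. The symptom-free calculation shows either direction is possible, and SAP 19.7.1 takes the worst value in each interval, so a longer window there cannot hide an abnormality.

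Nor is tolerability in general measured on two clocks. The TEAE window (SAP 19.1) and the worst-post-baseline window (SAP 6.4) are the same in both arms. AGS-16C3F exposure is also reported as number of doses and total mg, which a hold cannot inflate. SAP 19 plans no statistical comparison of safety data unless a section specifies one.

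Finally, a 3-weekly infusion and a twice-daily tablet cannot share one literal formula. That is fair: using the last infusion date alone would drop most of a cycle. It argues for a common principle with arm-specific arithmetic, not for two principles. None of these objections reaches the medication and eye-period rules, which carry no exception.

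**Conclusion.** The concern holds in a limited form. The medication and eye-period rules end treatment at the decision date in one arm and at the last dose in the other, so events in a final unresumed hold are classified differently by arm. For duration the defect is an internal contradiction: 35 extra days in the example on one reading, none on the other, and no stated end date on the latter.

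The reach is descriptive exposure, medication and eye-period tables. PFS, the one-sided 0.1 level, the 110-event target and its power are untouched. Censoring Set 2, which does use the decision date, applies it in both arms. Subjects on hold at cut-off but still on treatment are counted to cut-off in both arms. The size rests on an assumed dosing history and an assumed share of subjects with such holds, and the direction of any effect on symptom-free days is not established. It should be corrected before programming, but it does not threaten the trial's main conclusion.

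**What to change.** State one convention for subjects off treatment: treatment ends when the period covered by the last dose ends. For AGS-16C3F this is the earliest of last infusion + 20 days, decision date, death and data cut-off. For axitinib it is the last dose date. In the example both arms then have 42 days, and in the four-infusion history both have 84.

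Rewrite the two conflicting sentences of SAP 15.1.1.2 to match. Apply the convention in SAP 6.1, 14, 19.7.1, 19.7.2 and Appendix 2. Tabulate non-anticancer medications started from that date to Safety Follow-Up in the same way for both arms. While editing SAP 15.1.1.5, settle whether delay length subtracts 21 or 28 days.

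The cost is SAP wording and a few derivations; the main dates are already collected on the eCRF. The downside is that AGS-16C3F durations become slightly shorter.
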